## 8.2 Efficacy Assessments

For the efficacy assessments of pulmonary function, timed function tests, and hand held myometry, each site will have at least one and preferably two trained clinical evaluators who are qualified physical therapists and who will have undergone standardized training. They must be certified as capable of performing all clinical assessments as specified for this study. Their strength measures, results of lung function tests and timed function tests must match those of the trainer within set acceptability parameters that are detailed in the clinical evaluator manual. Other efforts to reduce variability, include making every effort to have each subject assessed by the same clinical evaluator for each type of assessment throughout the entire study. Assessments must be conducted in the same order at each visit as stated in the clinical evaluator manual and at approximately the same time of day throughout the study. Clinical evaluators will not have access to prior test results to avoid bias based on knowledge of previous data.

Clinical assessments conducted by the physical therapists will be monitored for quality control by an expert team of physical therapists. Videos will be uploaded to a cloud based secure storage facility for centralized review. Clinical evaluator performance will be documented by a report which is sent to the evaluators and stored in the site files as well as within the secure cloud-based facility. Informed consent for video review will be obtained from the subject.

## 8.3 Pharmacokinetic Assessments

Blood samples (at least 1 mL per sample) will be collected for determination of 21-desacetyl deflazacort and 6 $\beta$ -hydroxy-21-desacetyl deflazacort. Pharmacokinetic sample collection, processing, storage, and shipment will be performed according to instructions outlined in the PK laboratory manual separate from this protocol. 21-desacetyl deflazacort and 6 $\beta$ -hydroxy-21-desacetyl deflazacort plasma concentrations will be determined by the bioanalytical group of Celerion, Lincoln, Nebraska, USA, using a validated liquid chromatography with tandem mass spectrometry (LC-MS/MS) method. The lower limit of quantification of the LC-MS/MS method for simultaneous determination of 21-desacetyl deflazacort and 6 $\beta$ -hydroxy-21-desacetyl deflazacort is 1.0 and 0.5 ng/mL respectively.

The pre-dose blood draw will be taken within 2 hours before dosing. For timepoints up to 2-hours post dose, a window of  $\pm$  10 minutes will be allowed for blood collection. From 4 hours to 6 hours post samples, a window of  $\pm$  30 minutes will be allowed.

## 8.4 Adverse Events and Serious Adverse Events

### 8.4.1 Definition of an adverse events

An adverse event is any untoward medical occurrence associated with the use of a drug in humans, whether or not it is considered related to the drug. An AE can therefore be any unfavorable and unintended sign (including an abnormal laboratory finding), symptom, or disease in a study subject who is administered study drug in this study.

For this protocol, untoward medical occurrences that should be reported as AEs include the following:

1. All AEs during the course of treatment with study drug administration
2. All AEs resulting from medication misuse, abuse, withdrawal, or overdose, of study drug
3. All AEs resulting from medication errors such as dispensing or administration error outside of what is described in the protocol
4. Apparently unrelated illnesses, including worsening of a preexisting illness
5. Injury or accidents. Note that if a medical condition is known to have caused the injury or accident (a fall secondary to dizziness), the medical condition (dizziness) and the accident (fall) should be reported as 2 separate AEs. The outcome of the accident (hip fracture secondary to the fall) should be recorded in source documents.
6. Abnormalities in physiological testing or physical examination findings that require clinical intervention or further investigation (beyond ordering a repeat [confirmatory] test)
7. Laboratory or ECG abnormalities that require clinical intervention or further investigation (beyond ordering a repeat [confirmatory] test) unless they are associated with an already reported clinical event. Laboratory abnormalities associated with a clinical event should be captured in the source documents. Laboratory abnormalities not requiring clinical intervention or further investigation will be captured as part of overall laboratory monitoring and should not be reported as AEs.
8. A preexisting condition (eg, allergic rhinitis) must be noted on the appropriate eCRF for Visit 1 but should not be reported as an AE unless the condition worsens, or episodes increase in frequency during the AE reporting period. Diagnostic and therapeutic noninvasive and invasive procedures, such as surgery, should not be reported as AEs. However, the medical condition for which the procedure was performed should be reported if it meets the definition of an AE. For example, an acute appendicitis that occurs during the treatment with study drug should be reported as the AE and the resulting appendectomy should be recorded in the source documents and eCRF. If a surgical procedure was planned prior to entry into the study, and the surgery is not performed because of a worsening of a baseline condition, this should not be reported as an AE. Note that, as described in Section 8.4.2 any hospitalization occurring as the consequence of an AE during the study period should be reported as an serious adverse event (SAE).

Each AE is to be classified as serious or non-serious by the Investigator using medical and scientific judgment.

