#### **1.3 Benefit/Risk Profile**

Currently, treatment options for LGMD2I are limited. LGMD2I is a devastating disease and patients with this form of muscular dystrophy are at high risk for developing respiratory failure and cardiomyopathy (Narayanaswami 2014). Respiratory failure constitutes a major comorbidity, interfering with daytime cognitive function and negatively affecting quality of life (Narayanaswami 2014). In addition, ventilatory and oropharyngeal weakness can threaten survival through the risk of upper airway obstruction and/or bellows failure (Narayanaswami 2014).

Deflazacort carries the risks common to all corticosteroids, including immune suppression, decreased bone density, and endocrine insufficiency (see [Emflaza® \[deflazacort\] Prescribing Information](#)).

No definitive therapies are available for LGMD2I, and only a few clinical studies have assessed therapies for the treatment of LGMD2I ([Narayanaswami 2014](#)). To date no randomized, controlled clinical studies have been performed that evaluate treatment effect of corticosteroids in this patient population. Several case study reports suggest that corticosteroid therapy may improve the symptoms of the disease and possibly delay disease progression ([Darin 2007](#), [Svahn 2015](#), [Wang 2018](#)). In addition, preclinical studies in a LGMD2I mouse model found prednisolone treatment improved muscle pathology with significant reduction in muscle degeneration and enhanced functionality of  $\alpha$ -DG ([Wu 2016](#)).

Given the limited treatment options to slow the deterioration of muscle function in LGMD2I and findings from preclinical studies and case reports, it is reasonable to consider the use of deflazacort in treating patients with LGMD2I. Moreover, deflazacort has well established efficacy in DMD, and has been shown to delay DMD disease progression in patients ([Bello 2015](#), [McDonald 2018](#)). The safety profile of corticosteroids is well established in multiple indications, and safety concerns can be managed through monitoring, including bone health (as assessed by incidence of fracture and dual energy X-ray absorption [DEXA]) scans. Hence, the potential benefits of this study outweigh the potential risks to study subjects.

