### 6.1.2.2 *Safety Criteria for Adjustment or Stopping Dosing*

Unless an occurrence of an AE requires otherwise, the investigator is encouraged to maintain the same dose through the first 13 weeks of treatment due to the potential to confound the PK, safety, and efficacy evaluations. Dose adjustments are permitted as follows:

1. In order to maintain the weight-based dose of 0.6 mg/kg/day of deflazacort, if the subject has experienced weight gain that places them in the next higher weight band, the dose may be increased accordingly. If the subject has experienced an AE as described below, the Investigator may elect not to increase the dose despite weight gain.
2. At the discretion of the Investigator, the dose may be decreased to that of the next lower weight band in response to an AE. See recommendations below.
3. At the end of the study, subjects will switch from the study medication to an appropriate dose of a commercially available deflazacort or any other available corticosteroid. If the subject/Investigator does not wish to continue corticosteroid use, the dose of deflazacort must be reduced per Section 7.1 procedures.

Discontinuation of deflazacort during Period 1 of the study should be avoided unless clinically necessary. In the case of the development of predictable, deflazacort-related adverse effects, appropriate supportive care should be provided such that dosage can be maintained. Specific, standard of care recommendations for precautionary interventions for specific corticosteroid-related AEs are given below.

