### ***Bone Fractures Due to Osteoporosis***

Subjects who experience limb fractures should have fixation as directed by an orthopedic surgeon. Subjects who develop vertebral fractures can be treated with bisphosphonates (eg, pamidronate, 0.5 to 1 mg/kg/day intravenous for 3 days every 4 months). Subjects should not have a dosage adjustment due to the occurrence of fractures.

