### **8.4.5 Recording Serious and Non-serious Adverse Events**

All AEs (both serious and non-serious) that occur in subjects during the AE reporting period must be recorded, whether or not the event is considered drug related. In addition, any known untoward event that occurs subsequent to the AE reporting period that the Investigator assesses as possibly related to the investigational drug/product should also be recorded as an AE.

All AEs are to be recorded in the source documents and on the eCRF using concise medical terminology; whenever possible, terms contained in the Medical Dictionary for Regulatory Activities (MedDRA) should be employed. In addition, the following information should be recorded:

1. Indication of whether the event is serious or non-serious (see Section [8.4.2](#))
2. Relationship to study drug (see Section [8.4.2](#))
3. Severity of the event (see Section [8.4.7](#))
4. Onset date
5. Resolution date, or date of death
6. Action taken
7. Outcome of the event

Classification of the event as serious or non-serious determines the reporting procedures to be followed.

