**Table 7. Relationship of Study Drug to Adverse Event Relationship**

Relationship	Description
Probable	A clinical event in which a relationship to the study drug seems probable because of such factors as consistency with known effects of the drug; a clear temporal association with the use of the drug; improvement upon withdrawal of the drug; recurrence upon rechallenge with the drug; lack of alternative explanations for the event.
Possible	A clinical event occurring coincident with administration of the study drug and which may or may not be explained by concurrent disease or other drugs or chemicals. Information on drug withdrawal or rechallenge may be lacking.
Unlikely	A clinical event with a temporal relationship to the study drug exposure that does not preclude causality but for which there is a clear alternate cause that is more likely to have caused the adverse event than study drug. Such alternatives include a concomitantly administered drug, the subject's disease state, other medical conditions, or environmental factors.
Unrelated	A clinical event, for which a relationship to the study drug seems improbable because of factors such as inconsistency with known effects of the study drug, lack of a temporal association with study drug administration, lack of association of the event with study drug withdrawal or rechallenge, and/or presence of alternative explanations for the event. Alternative explanations might include a known relationship of the adverse event to a concomitant drug, medical history of a similar event, the subject's disease state, other medical conditions, or environmental factors.

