6.12.1 Adverse Events

Adverse events (AEs) will be classified as pre-treatment adverse event, treatment-emergent adverse event (TEAE) and post-treatment adverse event. Pre-treatment AE is defined as the AE occurring prior to the start of the deflazacort treatment.

TEAE is defined as the AE occurring or worsening on or after the first deflazacort dose and up to 30 days after the last deflazacort dose. Post-treatment AE is defined as the AE occurring after 30 days of the last deflazacort dose.

If a subject experience the same preferred term multiple times, the event will be counted only once and by the greatest severity.

TEAEs will be summarized by System Organ Class (SOC) and Preferred Term (PT) according to the Medical Dictionary for Regulatory Activities (MedDRA, version 23.1).

A treatment-related AE is defined as an AE as being possibly or probably related to the study drug. If an AE has a missing relationship it is assumed to be related to the study drug for analysis purposes.

An overall TEAE summary table will be provided with following information:

- The number of subjects with at least one TEAE
- The number of subjects with at least one treatment related TEAE
- The number of subjects with at least one Grade 3 or Grade 4 TEAE
- The number of subjects with a Grade 5 TEAE (Fatal)
- The number of subjects with at least one SAE
- The number of subjects with at least one TEAE leading to treatment discontinuation

QMD Ref: Worldwide-TMP-ST-005-7.0 Effective: 12Aug2019	Governing QMD: Worldwide-SOP-ST-001
Confidentiality Statement	
This document is the property of Worldwide Clinical Trials Inc. and may not be duplicated, copied, altered or removed from company without prior approval from Worldwide Quality Assurance or in compliance with Worldwide Standard Operating Procedures.	

Worldwide Clinical Trials Controlled Quality Management Document		
 WORLDWIDE CLINICAL TRIALS	Sponsor:	PTC Therapeutics, Inc
	Protocol Number:	PTCEMF-GD-004
STATISTICAL ANALYSIS PLAN		

- The number of subjects with at least one TEAE leading to dose reduction or interruption

In addition, the All TEAE by SOC and PT summary tables will be provided.

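### Protocol 8.4.1 item 5 sends a fracture caused by a fall to source documents without mentioning the eCRF, so such a fracture could be missing from the SAP's adverse event tables and listings

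*Protocol*

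**What the plan says.** Protocol 8.4.1 lists what sites should report as AEs. Item 5 covers injuries and accidents. Its example is a fall caused by dizziness: dizziness and the fall are two separate AEs. It then adds: "The outcome of the accident (hip fracture secondary to the fall) should be recorded in source documents".

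Other text on AE recording is broader:

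- Section 8.4.5: "All AEs are to be recorded in the source documents and on the eCRF using concise medical terminology". Table 9 likewise puts all serious and all non-serious AEs on the eCRF.
- Section 8.4.1 item 8, on diagnostic and therapeutic procedures, invasive or not: the procedure is not an AE, but "the medical condition for which the procedure was performed should be reported if it meets the definition of an AE".

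Protocol 1.3 argues that safety concerns can be managed through monitoring that includes bone health, "as assessed by incidence of fracture" and by DEXA. Protocol 3.2 lists fracture risk among the known harms of the drug class.

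SAP 6.12.1 states that "the All TEAE by SOC and PT summary tables will be provided", and adds by-subject AE listings. It has no separate summary or listing of fractures.

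**The concern.** Item 5 is the one instruction written for exactly this event, and its example leaves the fracture off the list of things to report. A site that follows it would enter the fall and stop there. The fracture would then have no term, date, severity grade or causality rating of its own, and would not reach the TEAE tables or the AE listings. Another site, following 8.4.5 or item 8, could enter the same injury as an AE, so capture could differ between sites.

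The subjects have proximal muscle weakness and take a corticosteroid, so a fall is a plausible route to a fracture, and the fracture matters for judging the drug. The error runs one way: item 5 can remove fractures from the reported count but cannot add any.

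**Working it through.** The documents give no figure on this point to reproduce, so the check is mainly a comparison of texts.

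1. **Count the events in item 5's example.** Three are named: dizziness, fall, hip fracture. Two are to be reported as AEs. The third goes to source documents.

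2. **What does source documents alone mean in this section?** Item 7 uses it for laboratory abnormalities tied to a clinical event already reported, which are not reported as separate AEs. Item 8, when it wants the appendectomy captured on the case report form, names source documents and the eCRF together. Read beside items 7 and 8, item 5 naturally means that the fracture is not a separate eCRF entry.

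3. **Is a fracture otherwise an AE?** Yes. It is an untoward medical occurrence under the general definition in 8.4.1, and an injury under the opening word of item 5. Section 8.4.5 and Table 9 then require it on the eCRF. If it is imaged, splinted or fixed, item 8 makes it reportable as the condition behind the procedure. The protocol therefore contradicts itself.

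4. **Do the other routes guarantee that the word fracture is entered?** Item 6 covers examination findings that need intervention or further investigation. The SAE criteria in 8.4.2 cover hospitalisation, significant disability and medically important events. These make it likely that something is reported, but no text says the term must be the fracture. Section 8.4.9 asks for the same AE term on the SAE form and the eCRF; both could say fall.

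5. **Does any other planned output recover it?** The only scheduled X-ray is of the lateral spine. SAP 6.12.7 concerns bone mineral density and tables of the DEXA or X-ray assessments performed. Neither picks up a hip or limb fracture.

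6. **Scale, for illustration only.** SAP section 1 gives 11 enrolled subjects. One fracture lost from the table changes the row by 1/N.
   - If all 11 received deflazacort: 1/11 = 9.1 percentage points.
   - The Safety Population counts only dosed subjects, so the step cannot be smaller. If only 8 were dosed (an assumption), it is 1/8 = 12.5 points.
   - Exact (Clopper-Pearson) 95% limits for 0/11: 0 to 1 − 0.025^(1/11) = 28.5%.
   - For 1/11: lower 1 − 0.975^(1/11) = 0.2%; upper, the 97.5% point of Beta(2, 10), = 41.3%.

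   The SAP plans no confidence intervals for AEs. These limits only show how little 11 subjects can say either way.

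**The case against.** The best reply is that item 5 excludes nothing. Items 7 and 8 say expressly when something should not be reported; item 5 does not, and an entry in source documents does not forbid one on the eCRF. The sentence also follows a note about accidents caused by a medical condition, so an ordinary trip or slip may fall under the plain injury rule. Item 8 reaches noninvasive and diagnostic procedures, so even a fracture that is only X-rayed and splinted has a route. Item 6 and the SAE criteria add more.

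All of this stands as a limit on the consequence. It rules out the inference that fall-related fractures will be lost as a rule, and the narrower inference that those neither operated on nor admitted have no route. It does not remove the contradiction: a site must choose between a specific example and a set of general rules.

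Three further inferences should be resisted:

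- **That 6.1.2.2 directly contradicts item 5.** It does say "recommendations for precautionary interventions for specific corticosteroid-related AEs are given below", and under fractures "Subjects who experience limb fractures should have fixation as directed by an orthopedic surgeon". But it is management advice under a heading about osteoporosis, not a recording rule. It shows that the protocol regards fracture as a steroid harm, and no more.
- **That Table 7 creates the causality problem.** Its category for events "for which there is a clear alternate cause that is more likely to have caused the adverse event than study drug" could be applied to any AE, including a fracture entered under its own term. What item 5 may cost is the chance to rate the fracture at all.
- **That a named endpoint is compromised.** Spine fracture on X-ray is collected separately, and hip or limb fracture is not a named endpoint.

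**Conclusion.** The point holds as an internal contradiction in the AE recording rules with a possible one-directional effect on the safety tables. A fall-related hip or limb fracture could be absent from the SAP 6.12.1 tables and listings, and could lack its own severity and causality rating, if a site follows item 5's example literally. The documents give no fall or fracture rate for this population and report no such event, so the number affected is unknown and may be zero.

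The 9.1-point step describes one hypothetical case and assumes that all 11 subjects were dosed; it is not an estimate of bias. The matter deserves correction because fracture is a known class harm, because the benefit/risk section relies partly on fracture incidence, and because checking is cheap.

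**What to change.** **Protocol, if it is revised or reused.** Replace the last sentence of item 5 with: *Any injury resulting from the accident (eg, hip fracture) should also be reported as a separate AE on the eCRF.*

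**Data management, now.** The sponsor decided on 23 July 2020 to end the study early, so rewording alone will not help the data already collected. Before database lock (the documents do not give its date), query source documents for each fall, injury or accident AE. Enter any fracture found as its own AE, with its own term, date, severity and causality.

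**SAP 6.12.1.** Add a listing or a count of subjects with any fracture on deflazacort.

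The recording rule belongs in the protocol and the query in data management; only the output belongs in the SAP. The cost is one query round on at most 11 subjects and one listing or small table, with no new procedure. If the query finds nothing, the zero has been checked rather than assumed.

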#### 8.4.2 Definition of a serious adverse events

An SAE is an untoward medical occurrence or effect associated with the use of a study drug at any dose, regardless of whether it is considered by the Investigator to be related to the study drug, which results in one of the following:

1. Results in death. This includes all deaths on treatment or within 30 days after last study drug administration, including deaths due to disease progression. Any death occurring later than 30 days following the last dose need not be reported as an SAE unless it is a result of an event that started within the period covered by the on-study definition. The reported AE should be the event that caused the death. In addition, any AE resulting in death that occurs subsequent to the AE reporting period and that the Investigator assesses as possibly related to the study drug should also be reported as serious.
2. Is life-threatening. This refers to an event in which the subject was at risk of death at the time of the event. It does not include an event that, had it occurred in a more severe form, hypothetically might have caused death.
3. Requires hospitalization or prolongation of existing hospitalization (excluding hospitalizations for administration of the study drug, procedures required by the study protocol, or treatment-related diagnostic procedures; other planned hospitalizations; or hospitalizations related only to progression of disease). Treatments in the emergency room for procedures such as hydration that do not require admitting the subject to the hospital and observational durations in the emergency room for less than 24 hours do not fall into this category.
4. Results in persistent or significant disability or incapacity or substantial disruption of the ability to conduct normal life functions, not related to cancer.
5. Any other medically important event that the Investigator or the sponsor judges to be serious or which is defined as serious by the regulatory agency in the local country. These are AEs that might not be immediately life-threatening or result in death or hospitalization but might jeopardize the subject or might require intervention to prevent one of the other outcomes listed above. Medical judgment should be exercised in deciding whether an AE is serious based on above definition. Examples of such events are intensive treatment in an emergency room or at home for allergic bronchospasm, blood dyscrasias or convulsions that do not result in hospitalization, or development of drug dependency or drug abuse.
6. A pregnancy resulting in spontaneous abortion, stillbirth, neonatal death, or congenital anomaly (including that in an aborted fetus).

Note that any SAEs occurring within 30 days after last study drug administration (end of study) should be reported to the sponsor if the Investigator becomes aware of them.

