### 8.4.9 Serious Adverse Event Reporting

All SAEs should be reported via the SAE report form to PTC Therapeutics within 24 hours of becoming aware of the event(s). In addition, the AE portion of the eCRF must also be completed.

The SAE report form should be signed by the Investigator; however, if the Investigator is unable to sign at the time of the event or within 24 hours, the form should be signed by the clinical staff member reporting the SAE (eg, the study coordinator). The SAE report form must be faxed or e-mailed to the PTC Therapeutics Pharmacovigilance Department or designee and to the site Institutional Review Board/Institutional Ethics Committee (IRB/IEC) (if required by local regulations) within 24 hours.

Follow-up information to the SAE should be clearly documented as “follow-up” in the SAE report form and must also be faxed or e-mailed to the same party. All follow-up SAE report forms for the event must be signed by the Investigator. Any source documents (eg, progress notes, nurses’ notes, laboratory and diagnostic test results, discharge summaries) provided to the sponsor should be redacted so that the subject’s name, address, and other personal identity information are obscured. Only the subject’s study number and initials are to be provided (in regions where the provision of such information is permitted). The information in the AE portion of the eCRF and the SAE report form(s) must match or be reconciled. Where the same data are collected, the forms must be completed in a consistent manner. For example, the same AE term should be used on both forms.

In the rare event that the Investigator does not become aware of the occurrence of an SAE immediately (for example, if a subject initially seeks treatment elsewhere), the Investigator is to report the event within 24 hours after learning of it and to document his/her first awareness of the AE.

The PTC Therapeutics Pharmacovigilance Department contact information for reporting SAEs is provided below. This information is also provided in the Study Manual and in the SAE report form.

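### Protocol 8.4.2 excludes admissions attributed only to disease progression from the SAE hospitalization criterion, in conflict with 8.4.1, so some respiratory or cardiac admissions can miss 24-hour reporting and the SAE outputs

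*Protocol*

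**What the plan says.** Protocol 8.4.2 lists the criteria that make an event serious. Item 3 is hospitalization, with several exceptions; the last reads "or hospitalizations related only to progression of disease". Item 1 of the same list covers deaths on treatment or within 30 days of the last dose, "including deaths due to disease progression".

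Protocol 8.4.1 lists what is to be reported as an AE. Item 4 reads "Apparently unrelated illnesses, including worsening of a preexisting illness". Item 8 says that a condition present at entry becomes an AE if it worsens. It ends with a note, cross-referring to 8.4.2, that "any hospitalization occurring as the consequence of an AE during the study period should be reported as an serious adverse event (SAE").

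Protocol 1.3 describes the disease setting: "patients with this form of muscular dystrophy are at high risk for developing respiratory failure and cardiomyopathy".

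Protocol 8.4.8 (Table 9) and 8.4.9 send SAEs, and not non-serious AEs, to the sponsor on the SAE form within 24 hours. SAP 6.12.1 plans an SAE row in the overall table of treatment-emergent AEs (TEAEs) and an SAE listing. Protocol 9.5.7.1 plans an SAE table by system organ class and preferred term.

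**The concern.** The two sections give a site different answers for the same admission. LGMD2I is an illness that every subject has at entry, so its worsening is an AE under 8.4.1, and an admission that follows from it is an SAE under item 8. Under 8.4.2 item 3 the same admission is not serious if the investigator holds progression alone responsible. A death from the same episode would be reportable.

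The disease makes this matter. Respiratory failure and cardiomyopathy are its named complications, so progression is a ready explanation for the admissions of most interest. The trial asks whether the drug slows progression, and its summaries have no comparator: SAP section 6 pools all deflazacort-treated subjects and leaves placebo-period data to listings. The attribution to progression therefore cannot be tested against a control group, yet it is what decides whether a report is sent.

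**Working it through.** The plan gives no figure on this point, so there is nothing to reproduce. The check compares the passages and follows one event through the reporting chain.

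**Step 1. Is the admission an AE?** Yes, under 8.4.1 items 4 and 8: a pre-existing illness has worsened.

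**Step 2. Is it an SAE under 8.4.1?** Yes, under the closing note of item 8, which states no exception for progression.

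**Step 3. Is it an SAE under 8.4.2?**

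| Criterion in 8.4.2 | Exclusion for disease progression? |
|---|---|
| Item 1, death | No; progression deaths are expressly counted |
| Item 2, life-threatening | No |
| Item 3, hospitalization | Yes, if related only to progression |
| Item 4, disability | No (only a qualifier about cancer) |
| Item 5, medically important | No; the investigator or sponsor decides |

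So the answer is no only if three conditions hold together: the admission is attributed to progression, nothing else contributed, and no other item applies.

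**Step 4. Where does such an event go?**
- 24-hour SAE form: no (Protocol 8.4.8 Table 9; 8.4.9).
- SAE row and SAE listing: no (SAP 6.12.1).
- SAE table: no (Protocol 9.5.7.1).
- AE record on the eCRF: yes (Protocol 8.4.8 Table 9).
- TEAE tables, if it arose on deflazacort or within 30 days of the last dose: yes (SAP 6.12.1). If graded 3 or 4, also the Grade 3 or 4 row and the matching listing.

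**Step 5. Illustration of weight.** Inputs: 11 subjects enrolled (SAP section 1) and 30 planned (Protocol 9.2). Assumptions: every enrolled subject is in the Safety Population; one subject has such an admission and no other SAE. Proportion = x/n, with exact (Clopper-Pearson) 95% intervals. For x = 0 the upper limit is 1 − 0.025^(1/n).

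| n | Exclusion applied | Counted as an SAE |
|---|---|---|
| 11 | 0/11 = 0.0% (0.0 to 28.5%) | 1/11 = 9.1% (0.2 to 41.3%) |
| 30 | 0/30 = 0.0% (0.0 to 11.6%) | 1/30 = 3.3% (0.1 to 17.2%) |

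The row counts subjects. If the subject already has another SAE, the row does not move. The exclusion can therefore lower the row or leave it unchanged, and cannot raise it.

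**The case against.** The strongest reply is that the exclusion is narrow and the contradiction partly a matter of reading.

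- **Other routes to seriousness.** Item 2 covers any event that "Is life-threatening. This refers to an event in which the subject was at risk of death at the time of the event", and item 5 covers "Any other medically important event that the Investigator or the sponsor judges to be serious". Acute respiratory failure or cardiac decompensation could well qualify under either. This stands and limits the point. It does not close the gap: a subacute admission for declining function need not carry a risk of death at the time, and item 5 is discretionary.
- **The cross-reference.** The note in 8.4.1 item 8 refers to 8.4.2, so it can be read as accepting the exclusion. That softens the conflict. But the note presents 8.4.2 as covering every admission that follows from an AE, which it does not, so a site still meets two rules.
- **AE is not SAE.** 8.4.1 item 4 defines an AE and says nothing about seriousness, and treating deaths and admissions differently is a possible choice. Both are true. The conflict rests on item 4 read together with item 8; the death criterion shows uneven treatment, not contradiction by itself.
- **The event is still recorded.** True, as step 4 shows. The medical monitor also hears of AEs that lead to dose interruption (8.4.13) and of treatment discontinuations (7.2). An admission during which dosing continues reaches the monitor by neither route.
- **Eligibility.** Protocol 4.3 excludes ejection fraction below 30%, full-time ventilation and clinically significant pulmonary or cardiovascular disease. This makes such admissions less likely but does not rule them out.

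A reader might infer that known drug effects, such as infection, hypertension or acute myopathy, are removed by this exclusion. The text does not support that. An admission with such a contribution is not due only to progression, and the protocol mentions acute myopathy in connection with concomitant neuromuscular blocking drugs (6.5.2).

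**Conclusion.** The point holds in a limited form. Protocol 8.4.1 and 8.4.2 do not give sites one rule for an admission attributed solely to LGMD2I progression. Where no other criterion applies, that admission can miss 24-hour reporting and every SAE output, while remaining a non-serious AE.

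A reader might go further and conclude that respiratory and cardiac admissions on drug escape SAE reporting in general, or that the SAE rate is understated by a known amount. Neither follows. The exclusion applies to one criterion and to one attribution, and the documents report no such admission. The shift from 0% to 9.1% is an illustration that assumes one affected subject with no other SAE and a Safety Population of 11. The population could be smaller, because it requires a dose of deflazacort and placebo subjects moved to open-label treatment by choice. Only the direction is certain: never upward.

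The correction is worth making because it is cheap and the summaries offer no comparator against which to judge the attribution.

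**What to change.** 1. Delete the progression exclusion from Protocol 8.4.2 item 3, so that it agrees with 8.4.1 item 8. An admission that follows from worsening LGMD2I is then reported as an SAE, with the clinical event (for example, respiratory failure) as the term. The investigator states the relationship to study drug under Table 7, so reporting the event does not imply that the drug caused it.
2. As clean-up, remove the cancer qualifier from 8.4.2 item 4, which has no application in this trial. No effect on any result is claimed for this.
3. Enrolment has ended at 11 subjects, so a change of wording alone will not reach events already classified. Have sites check AEs recorded as non-serious, against source documents, for admissions attributed to progression, and do so before the SAE row, listing and table are final.

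The cost is a protocol amendment with ethics review (Protocol 10.1.1) in a study that the sponsor has already decided to end early, a short source check in 11 subjects, and a few extra SAE forms if any such admission is found.
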